### **3.4 Study Duration**

The maximum duration of a subject's participation in the study is approximately two years.

## **4 VACCINES**

All subjects will receive an FDA approved and recommended influenza vaccine in each season. Any individual with a contraindication to influenza vaccination will be unable to participate in the study. The four influenza vaccines that will be used in this study are 1) IIV3 (Fluvirin, Seqirus), 2) HD-IIV3 (Fluzone High-Dose, Sanofi Pasteur), 3) aIIV3 (Fluad, Seqirus) and 4) RIV4 (FluBlok, Protein Sciences). Vaccines will be stored and administered according to the manufacturer's package insert (Fluvirin:

<http://www.fda.gov/downloads/BiologicsBloodVaccines/Vaccines/ApprovedProducts/UCM123694.pdf>, Fluzone High-Dose:

<http://www.fda.gov/downloads/BiologicsBloodVaccines/Vaccines/ApprovedProducts/UCM305079.pdf>, Fluad:

<http://www.fda.gov/downloads/BiologicsBloodVaccines/SafetyAvailability/VaccineSafety/UCM474387.pdf>)FluBlok:

<https://www.fda.gov/downloads/biologicsbloodvaccines/vaccines/approvedproducts/ucm524684.pdf>

## **5 SELECTION OF STUDY SUBJECTS**

### **5.1 Inclusion Criteria**

Subjects must meet all of the following criteria to be eligible to participate:

- 1) Age 65 through 74 years at the time of enrollment and are ambulatory and live in Marshfield, Wisconsin or surrounding communities.
- 2) Willing and able to give informed consent prior to study enrollment.
- 3) Able to comply with study requirements.

## **5.2 Exclusion Criteria**

Subjects will be excluded if they fulfill any of the following criteria:

- 1) Prior receipt of 2016-17 (or 2017-18 for participants recruited in Fall 2017) influenza vaccine.
- 2) Current participation in another clinical trial.
- 3) Presence of a contraindication to influenza vaccines as described by the Advisory Committee on Immunization Practices.

## **6 STUDY PROCEDURES**

### **6.1 Enrollment Period**

Enrollment in this study will begin when influenza vaccine is available through the Marshfield Clinic, typically in August or September 2016, and will continue until the target sample size for each group is reached or all eligible adults have been contacted with the goal of completing all baseline study visits by the end of October 2016. The second enrollment period for the additional 30 subjects will follow the same recruitment procedures in Fall 2017.

### **6.2 Recruitment**

A recruitment letter that includes information on the FDA approved influenza vaccines used in this study will be sent to a sample of individuals aged 65-74 years who receive outpatient care from Marshfield Clinic facilities. Additional mailings will be sent, as needed, to additional patients who receive outpatient care from Marshfield Clinic facilities in batches until the target sample size in each group is reached. Marshfield Clinic patients who do not receive a recruitment letter but would like to participate in the study may participate provided they meet study eligibility criteria.

The letter will be followed by telephone contact within 10 days to assess interest, screen for contraindications to any vaccine, answer questions, and schedule a pre-vaccination appointment for those who have no contraindications and give initial verbal consent. Study visits will be scheduled at convenient times for the enrollee and to allow for efficient processing of blood samples (see additional detail in laboratory methods).

### **6.3 Study Visit Procedures**

Participants enrolled in the first season will have 6 scheduled study visits over an approximately 18 month period. At each visit, all participants will have a blood draw (20 mL [4 teaspoons]) for

evaluation of serologic response. Influenza vaccine will be administered at visit 1 and 4, prior to each influenza season. Participants will have a maximum of 6 blood draws during the study period.

Participants enrolled in Fall 2017 will have 3 scheduled study visits over an approximately 6 month period. At each visit, participants will have a blood draw (20 mL [4 teaspoons]) for evaluation of serologic response. Influenza vaccine will be administered at the enrollment visit (Study Visit 4).

### **6.3.1 Visit 1: Enrollment and Vaccination – Approximately 60 minutes**

Research staff will meet with eligible individuals to review study requirements and obtain written consent. A brief questionnaire may be administered to obtain additional information regarding demographics and relevant exposure and medical history. We will also request permission from individuals to access their electronic medical record in order to obtain data related to medical history, medication use, and vaccination history. The remaining study visits will be scheduled.

#### **6.3.1.1 Blood draw**

All participants will have a baseline blood draw for measurement of antibody titers (20 mL [4 teaspoons]), hemagglutination inhibition [HI] and other assays (see below). Serum from the samples will be prepared, frozen, and tested per current protocol (see laboratory methods). Additional measures of humoral immune function may also be examined.

#### **6.3.1.2 Influenza vaccine**

Individuals will receive either 1) IIV3, 2) HD-IIV3, or 3) aIIV3 according to a pre-assigned randomization scheme. Trained research staff will administer all vaccines.

Individuals with fevers will be rescheduled regardless of the vaccine to be received. Vaccinations will be recorded in the electronic immunization registry, and vaccine information sheets will be provided.

### **6.3.2 Visit 2: Day 28 Post-Vaccination, Year 1 – Approximately 30 minutes**

All participants will have a visit with blood draw at 28 ( $\pm 5$ ) days (20 mL [4 teaspoons]) for evaluation of serologic response. Research staff will also ask for the best time to call during the illness surveillance phase of the study.

### **6.3.3 Visit 3: 6-month Post-Vaccination, Year 1 – Approximately 30 minutes**

All participants will be scheduled to collect a 6-month post-vaccination serum specimen at approximately 182 ( $\pm 10$ ) days following receipt of the 2016-17 influenza vaccine to evaluate serologic response. The blood draw will be 20 mL (4 teaspoons).

### **6.3.4 Visit 4: Year 2 Vaccination – Approximately 40 minutes/Enrollment and Vaccination of New Recruits – Approximately 60 minutes**

#### **6.3.4.1 Year 2 Vaccination**

All participants who received the 2016-17 high dose trivalent inactivated influenza vaccine and 2016-17 aIIV3 at enrollment will receive the same vaccine type at this visit (for the 2017-18 season). Participants who received 2016-17 standard dose inactivated influenza vaccine at enrollment will be randomized to receive high dose trivalent inactivated influenza vaccine, aIIV3 or RIV4 at this visit (for the 2017-18 season). Prior to vaccination, all participants will have a blood draw to evaluate serologic response. The blood draw will be 20 mL (4 teaspoons).

Individuals with fevers will be rescheduled regardless of the vaccine to be received. Vaccinations will be recorded in the electronic immunization registry, and vaccine information sheets will be provided.

#### **6.3.4.2 Enrollment and Vaccination of New Recruits**

Research staff will meet with eligible individuals to review study requirements and obtain written consent. A brief questionnaire may be administered to obtain additional information regarding demographics and relevant exposure and medical history. We will also request permission from individuals to access their electronic medical record in order to obtain data related to medical history, medication use, and vaccination history. The remaining study visits will be scheduled.

All participants will have a baseline blood draw for measurement of antibody titers (20 mL [4 teaspoons]), hemagglutination inhibition [HI] and other assays (see below). Serum from the samples will be prepared, frozen, and tested per current protocol (see laboratory methods). Additional measures of humoral immune function may also be examined. Participants will receive either 1) HD-IIV3, 2) aIIV3, or 3)RIV4 according to a pre-assigned randomization scheme. Trained research staff will administer all vaccines.

Individuals with fevers will be rescheduled regardless of the vaccine to be received. Vaccinations will be recorded in the electronic immunization registry, and vaccine information sheets will be provided.

### **6.3.5 Visit 5: Year 2, 1-month Post-Vaccination – Approximately 30 minutes**

All participants will have a visit with blood draw at 28 days (20 mL [4 teaspoons]) for evaluation of serologic response.

### **6.3.6 Visit 6: Year 2, 6-month Post-Vaccination – Approximately 30 minutes**

All participants will be scheduled to collect a 6-month post-vaccination serum specimen in year 2 at approximately 182 ( $\pm 10$  days) days following receipt of the 2017-18 influenza vaccine to evaluate serologic response. The blood draw will be 20 mL (4 teaspoons).

### **6.3.7 Illness Surveillance**

During both influenza seasons, enrolled subjects will be followed prospectively to monitor for influenza illness. Participants will receive a weekly call from an interviewer to ask approximately 5 screening questions regarding presence of influenza like illness or respiratory symptoms including cough and duration of illness. A call list will be generated each week. The timing of the influenza season (surveillance phase) will depend on observations of influenza activity in the community and state-wide. We anticipate the surveillance period to be approximately November 1 through April 1 of each season. A reminder letter regarding the start of this phase of the study will be sent to enrollees approximately two weeks prior to the start of telephone calls.

“New onset” will require a period free of symptoms, or with baseline symptoms, and at least 14 days from onset of previous illness to differentiate an episode from any prior illness. When a new acute respiratory illness is reported and confirmed, an appointment to obtain a combined nasal and oropharyngeal (throat) swab for influenza testing will be scheduled within 7 days of illness onset if a participant reports an acute respiratory illness. Subjects will be asked to come to the clinic to obtain the respiratory sample, but home visits by research staff may also be available for subjects who are unable to come to the clinic.

Subjects will continue to receive weekly telephone calls for ascertainment of respiratory symptoms. Subsequent weekly calls for persons with recently reported acute respiratory illness will document resolution, or return to baseline, of symptoms.

## **6.4 Data Collection**

In addition to data collected through the enrollment survey, we will also electronically abstract data on vaccination and medical history from the immunization registry and electronic medical record.

### **6.4.1 Influenza Vaccination Status**

The availability and types of influenza vaccines vary from season to season. Vaccination status and vaccine types received will be obtained for prior seasons for all participants.

We have previously validated the use of the local immunization registry at Marshfield Clinic, RECIN, to correctly categorize receipt of influenza vaccine. Since RECIN exchanges records with the Wisconsin Immunization Registry, all vaccines administered by public health immunization providers will be identifiable. Immunization records have sufficient detail to

distinguish inactivated vaccine types, and to distinguish different manufacturers and lot numbers.

#### **6.4.2 Medical Record Review**

We may abstract medical records for participants. The goal of the abstraction will be to identify potential risk factors for no or low immune response to vaccination or vaccine failure. The elements that may be extracted electronically from medical records include: dates of medical visits for acute respiratory illness, tests and procedures performed, high risk conditions, influenza vaccination status in prior seasons, and patient demographics.

## **7 SPECIMEN COLLECTION AND HANDLING**

All blood samples will be collected at the Marshfield Clinic Central Laboratory by trained staff. The blood samples will be collected using Vacutainer tubes, with uniformly colored tops according to type of processing (e.g., red tops for serum), and appropriately labeled with a uniform scheme (including study ID and collection time point). Up to 20 mL blood will be collected at each visit.

Nasal and throat swabs will be collected by research staff who have been trained on the proper technique for collection of nasal and throat swabs. Research staff must demonstrate use of proper techniques before they are allowed to collect samples by study participants. Sample quality (human RNase P) will be monitored by RT-PCR to ensure adequate sample collection procedures.

To support better understanding of the immune response following influenza vaccination, specimens will be banked for future studies that might involve respiratory illnesses.

### **7.1 Serum**

For serum collection, whole blood drawn in a tube without anticoagulant will be left at room temperature for a minimum of 30 minutes and maximum of 2 hours. The samples will then be placed at 4° C. Samples will be processed within 24 hours of collection, and ideally the following morning for these afternoon/evening appointments. Tubes will be placed in a table-top centrifuge and serum will be clarified by centrifugation at 3000 rpm for 10 minutes at 4° C. Serum will be aliquotted into labeled, aliquot specific, cryovials with an adjustable pipettor. Aliquot size will be determined based on cross-site decisions. Serum will then be stored at -80°C in labeled fiberboard boxes and stored in the Marshfield Clinic Research Institute Integrated Research and Diagnostic Laboratory per current protocol until shipping. Once all participants have been enrolled and have completed all required blood draws, batched samples will be shared with collaborators at the CDC (or their designee) in order to conduct serologic assays.

## 7.2 Swabs

Combined nasal and oropharyngeal (throat) swabs for influenza testing will be collected by trained research coordinators. The nasal swab is quick and painless, and we have found that it is acceptable and well-tolerated. The nasal swab is collected by inserting a large Dacron or rayon tipped swab into one nostril to a depth of 1-2 cm. It is rotated gently against the septum for 3-5 seconds and then withdrawn. The throat swab is obtained by swabbing both tonsils and the posterior oropharynx. A sterile polyester-tipped applicator will be used for swab collection. The swab tips are immediately placed in M4-RT viral transport media and labeled. Specimens will be refrigerated or held on ice until they are transported to the laboratory on the same day.

## 8 LABORATORY METHODS

Blood samples from each study subject will be drawn for influenza serology testing at each of the six scheduled study visits. Hemagglutination inhibition (HI) antibody titers will be determined for all subjects at all time-points. Testing for virus neutralizing antibody titers, neuraminidase antibody mediated inhibition titers, and anti-human CD107a antibody titers will depend on HI results. Serologic parameters will include geometric mean titers (GMT), mean fold rise (MFR), seroresponse rate (SRR), and seroprotection rate (SPR) by vaccine group. Additional measures of humoral immune function may also be examined.

A brief description of each serological assay is provided in the following sections.

### 8.1 Hemagglutination Inhibition Antibody Testing

Serum samples from all subject collected at each of the 6 study visits will be tested by hemagglutination inhibition (HI) assays to estimate antibody titers against the 2016-17 vaccine strains and representative strains of circulating influenza viruses that are antigenically or genetically different during 2016-17 season in year 1 (visits 1, 2, 3 and 4) and 2016-17 and 2017-18 vaccine strains and representative strains of circulating influenza viruses that are antigenically or genetically different during 2017-18 season in year 2 (visits 4, 5, and 6) using standard techniques. Each serum sample is tested in duplicate and the final titer is the geometric mean titer (GMT) of the duplicate titers. HI testing will be conducted at CDC or by a CDC-designated laboratory.

### 8.2 Microneutralization Antibody Testing

Virus neutralization titers will be determined by a standard microneutralization (MN) assay, which is a highly sensitive and specific assay for detecting virus-specific neutralizing antibodies to influenza viruses. Testing for MN titers will depend on the circulating virus for each season. Each serum sample will be tested in duplicate and the final titer is the geometric mean titer (GMT) of the duplicate titers. MN testing will be conducted at CDC.

### **8.3 Neuraminidase Antibody Testing**

Testing to assess neuraminidase antibody mediated inhibition of influenza viruses with the neuraminidase inhibition assay (NAI) will depend on HI responses. Neuraminidase inhibition assays will be conducted at CDC using standard techniques.

The NAI assay, also known as the enzyme-linked lectin assay, measures antibodies that inhibit the enzymatic activity of viral neuraminidase, utilizing a reassortant influenza virus with a mismatched hemagglutinin (H6 subtype), to avoid interference by HA-specific antibodies, and neuraminidase from vaccine reference viruses. The percent inhibition of neuraminidase enzymatic activity at each serum dilution is calculated by comparison with values from virus control wells (virus but no serum); end-point NAI titers are calculated as the reciprocal of the highest dilution with at least 50% inhibition.

### **8.4 Antibody Dependent Cellular Cytotoxicity (ADCC) Analysis**

A modified influenza HA-specific antibody-dependent cell-mediated cytotoxicity natural killer (NK) cell activation assay will be quantified using a modified ADCC natural killer (NK) cell activation assay. Testing for ADCC will depend on baseline responses as measured by HI. Serially diluted human serum samples are added to wells containing recombinant HA and mixed with a human NK cell line and mouse anti-human CD107a antibody to measure CD107a expression on NK cells stimulated by ADCC antibodies present in sera. The results are expressed as endpoint titers, for example, the highest serum dilution that achieved the 3% of the arbitrary threshold. Each serum sample is tested in duplicate and the final titer is the geometric mean titer (GMT) of the duplicate titers. ADCC testing will be conducted at CDC.

### **8.5 RT-PCR**

Nasal and oropharyngeal (throat) swabs will be combined and tested using real-time reverse transcription polymerase chain reaction (RT-PCR) by staff from Marshfield Clinic Research Institute Integrated Research and Diagnostic Laboratory. CDC primers, probes, and procedures will be used for this assay. This PCR assay was developed and evaluated by CDC. Standard operating procedures for RT-PCR have been developed and will be followed. Total nucleic extractions will be performed using the Roche MagNA Pure Total Nucleic Acid Kit (Roche Diagnostics, Indianapolis, IN) on 200 µl of clinical samples. This is a high throughput, automated magnetic bead technology. Real-time RT-PCR will be performed on nucleic acid extracts using the LightCycler® Real-Time PCR System (Roche Diagnostics, Basel, Switzerland). The RT-PCR assay is a TaqMan® based real-time detection of the matrix protein (M1) of influenza A and the non-structural protein 1 (NS1) of influenza B. Both have been shown to be highly conserved, representing effective targets for detection. For each sample, the initial RT-PCR amplifies nucleic acid for type A and type B. The human RNase P gene primer and probe set serves as the internal positive control for human RNA. Samples positive for influenza A will be retested for subtype identification. These include primers for H1N1pdm09, and H3. Samples positive for influenza B will be further tested for B lineage.

Standard laboratory safeguards have been incorporated into the protocol to decrease the risk of carryover amplicon contamination. These include the use of uracil glycosylase, three separate unidirectional work flow areas, and laboratory surface decontamination products to eliminate any residual DNA/RNA.

## **9 PARTICIPANT COMPENSATION**

Participants will be compensated for the time and effort required to participate in this study. Each participant will receive a \$50 gift certificate for each blood sample provided (up to \$300 total), and a \$20 gift certificate for each combined nasal and oropharyngeal swab sample provided.

## **10 SHARING OF LABORATORY SPECIMENS AND DATA**

Marshfield Clinic Research Institute will share participant samples (serum and swabs) with CDC, or a laboratory designated by CDC. Record review and vaccination history data will also be shared with CDC, with appropriate privacy measures in place.

## **11 DATA MANAGEMENT**

### **11.1 Recording and Collection of Data**

Microsoft Access will be used for enrollment and data management. Research coordinators will carry tablet computers to access the Access database on the secure wireless network. Staff will use Access to assess eligibility, schedule and enroll patients, and track study visits. Microsoft Access has robust procedures to ensure accurate and complete data collection. Access will require documentation of informed consent, responses to all inclusion and exclusion criteria, specimen collection dates, and vaccination information (date, type, manufacturer, and lot number). Radio buttons, pick lists and pre-programmed data checks will be used to ensure valid data entry. Access records will be exported to SAS files for final analyses. REIN immunization records will be merged with Access enrollment records to define exposure (vaccination) status.

Reports will be generated on a regular basis to track recruitment, enrollment, and study visit completion and shared with collaborators during bi-weekly conference calls.

### **11.2 Data Quality Assurance**

Study data will be entered by trained study staff. The study programmer will monitor and review the study databases regularly. The study programmer will run a series of quality checks and validation to look for missing, incomplete, or inconsistent data. Any identified data issues will be reconciled with study staff prior to finalization of the dataset and analysis.

## **12 STATISTICAL CONSIDERATIONS**

### **12.1 General**

Demographic and baseline characteristics will be summarized by vaccine group for all subjects. Continuous variables will be presented by summary statistics (e.g., mean, and standard deviation (SD)) for non-immunogenicity endpoints, and geometric means and their 95% confidence interval for the immunogenicity endpoints. Categorical variables will be presented by frequency distributions; i.e., frequency counts and percentages for the non-immunogenicity endpoints, and the percentages and their 95% confidence intervals for the immunogenicity endpoints.

### **12.2 Analyses Addressing Objectives**

#### **12.2.1 Analyses of Primary Objectives**

After log transformation of the antibody titers, geometric mean antibody titers (GMT) pre- and post- vaccination will be compared within subjects by vaccine type. For the primary aim, adults receiving high dose trivalent inactivated influenza vaccine will be compared with those receiving aIIV3.

The mean and standard deviation of log titers will be calculated. Linear mixed-effects models will be used to adjust for variables such as age, given the potential for small differences in age and the known difference in GMT by age, baseline antibody titer and prior season vaccination status. The mean fold rise (MFR), defined as the mean of the ratio of post vaccination GMT and pre-vaccination GMT for each subject, between the groups will be computed from mixed-effects model along with its associated 95% confidence interval (CI). For the declaration of non-inferiority of GMT between groups, the lower bound of the adjusted 95% CIs for the GMT ratios will be determined for each strain.

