## **2 STUDY OBJECTIVES**

### **2.1 Primary Objectives**

- Compare immune responses to vaccine and drifted viruses as measured by hemagglutination inhibition (HI) among persons aged 65-74 years vaccinated with one of two licensed influenza vaccines recommended for this age group specifically formulated to increase immune response to vaccination: HD-IIV3 or allIV3 approximately 28 days, 6 months, and 12 months after receipt of the 2016-17 vaccine.
- Compare immune responses to vaccine and drifted viruses as measured by HI among subjects after repeat influenza vaccination (2016-17 and 2017-18) with HD-IIV3 and allIV3 approximately 28 days and 6 months after receipt of the 2017-18 vaccine.

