### 3 STUDY DESIGN

#### 3.1 Design

This is a randomized, open-label serologic study with enrollment of up to 180 adults aged 65-74 years in the first year (2016-17) and an additional 30 adults in the second year (2017-18) for a total of 210 across two years, at Marshfield Clinic Research Institute (MCRI). Subjects will be recruited from community-dwelling individuals who receive their inpatient and outpatient care from Marshfield Clinic facilities.

Randomization to one of three licensed influenza vaccine groups in the first year (2016-17) will be stratified by prior receipt of the 2015-16 influenza vaccine. The randomization algorithm will target enrollment of approximately 25% of subjects in the unvaccinated in 2015-16 stratum. It is anticipated that a percentage of the randomized study subjects may not complete the study.

Participants will be randomized to receive IIV3, HD-IIV3, or aIIV3 at their baseline study visit to ensure an appropriate minimum number of subjects receive high dose and adjuvanted vaccines in 2016-17 for analyses. Participants will be grouped according to vaccination type (standard dose, high dose or adjuvanted vaccine) received during the 2016-17 season (**Table 1**). All subjects enrolled in Fall 2016 will have a baseline serum blood draw, a second serum blood draw 28 ( $\pm 5$ ) days after vaccination and 6 months after vaccination in each season (2016-17 and 2017-18). In Fall 2017, participants who received HD-IIV3 and aIIV3 in Fall 2016 will receive the same vaccine type. Participants who received IIV3 will be randomized to receive HD-IIV3, aIIV3, or RIV4 for the 2017-18 season.

An additional 30 adults who received IIV3 in the 2016-2017 season will be recruited in Fall 2017. Newly recruited participants will be randomized to receive HD-IIV3, aIIV3, or RIV4 for the 2017-18 season and will have serum blood draw before vaccination, 28 ( $\pm 5$ ) days after vaccination and 6 months after vaccination.

Table 1. 2016-17 Vaccine Randomization & Blood Draw Scheme with Proposed ID numbering

	Group	2016-17 Vaccine	2017-18 Vaccine	Total
65-74 years	A	2016-17 HD-IIV3	2017-18 HD-IIV3	60
	B	2016-17 aIIV3	2017-18 aIIV3	60
	C1	2016-17 IIV3	2017-18 high dose trivalent inactivated influenza vaccine	30
	C2	2016-17 IIV3	2017-18 aIIV3	30
	C3	2016-17 IIV3	2017-18 RIV4	30
		Total		210

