## 3.3 Randomization Procedure

We will use stratified block randomization to ensure more even distribution of subjects with prior receipt of 2015-16 influenza vaccine. Subjects will be stratified based on receipt of 2015-

16 influenza vaccine. Within each group (vaccinated or unvaccinated in 2015-16), sequential enrollment numbers will be randomly assigned to each vaccine group in random blocks ranging from four to eight. This will ensure proper distribution of subjects across vaccine group assignment.

In Fall 2017, only participants who received IIV in 2016-17 will be randomized. We will use stratified block randomization and subjects will be stratified based on participation in this study during the 2016-17 season (previously participated or new recruit).

This is an open-label study, therefore the vaccine type will be known to the participant. Trained research staff will prepare and administer the influenza vaccine. Randomization to vaccination type will occur at the participant's first study visit after eligibility is confirmed and informed consent obtained. Those enrolled in year 1 who receive IIV3 will be randomized a second time at their fourth visit.

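### Does leaving the visit for the baseline titer unnamed put the year-2 comparison of repeat HD-IIV3 with repeat aIIV3 at risk?

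*Combined protocol and SAP*

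**What the plan says.** Section 2.1 sets two primary HI comparisons of HD-IIV3 with aIIV3. The first is made "approximately 28 days, 6 months, and 12 months after receipt of the 2016-17 vaccine". The second is made "among subjects after repeat influenza vaccination (2016-17 and 2017-18) with HD-IIV3" or with aIIV3, about 28 days and 6 months after the second dose (visits 5 and 6).

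Section 12.2.1 gives one model description for both. It adjusts for variables such as age and cites "the known difference in GMT by age, baseline antibody titer and prior season vaccination status". It then takes non-inferiority from the lower limit of the adjusted 95% interval, strain by strain. No visit is attached to the baseline titer.

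Groups A (HD-IIV3 in both years) and B (aIIV3 in both years) are randomised at visit 1. Section 3.3 adds: "In Fall 2017, only participants who received IIV in 2016-17 will be randomized".

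Section 8.1 sets the HI panel by visit. The first panel is for the "2016-17 season in year 1 (visits 1, 2, 3 and 4) and 2016-17 and 2017-18 vaccine strains" belong to the second, together with circulating strains that are "different during 2017-18 season in year 2 (visits 4, 5, and 6) using standard techniques". So 2016-17 strains are tested at visits 1 to 4. Vaccine strains of both seasons and 2017-18 circulating strains are tested at visits 4 to 6.

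On the word baseline, section 3.1 says "All subjects enrolled in Fall 2016 will have a baseline serum blood draw", and section 6.3.1.1 says of visit 1: "All participants will have a baseline blood draw for measurement of antibody titers". Section 6.3.4.2 repeats that sentence at visit 4 for the Fall 2017 recruits. Section 6.3.4.1 describes the returning participants' visit-4 draw only as taken before vaccination.

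**The concern.** For A versus B, the visit-4 titer is measured about a year after randomisation and is an outcome of the 2016 vaccine. Section 2.1 makes the 12-month titer part of a primary comparison. Conditioning on it removes the part of the year-2 difference that is carried by antibody persistence. What remains is the response to the second dose given the pre-dose titer, which is not the randomised comparison of two-year regimens.

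A strain tested only at visits 4 to 6 has no other planned same-strain titer before the second dose. An analyst who wanted a same-strain covariate would be drawn to visit 4. If the groups differ there, the adjusted ratio and its interval shift against the group whose antibody lasted better, in a primary objective and in the interval used for non-inferiority. The study is open-label and the visit is not named, so the choice could also be made after titers are seen, or differ between carried-over and new strains.

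**Working it through.** **The plan's own figure.** The only design figure is in section 12.3: over 90% power with 60 per group for a GMT difference of about 20%. It gives no SD or alpha, so it cannot be reproduced, and this point does not depend on it.

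**Where each candidate titer stands for A versus B**

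| Strain | Visit-1 titer planned? | Visit-4 titer planned? |
|---|---|---|
| 2016-17 vaccine strain | Yes, before randomisation | Yes, after randomisation |
| Strain new to the year-2 panel | No | Yes, after randomisation |

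For the first row, the protocol's usage (sections 3.1 and 6.3.1.1) points to visit 1, and no problem arises. The second row is the only exposed case. The documents do not name any strain in it. C1 versus C2 versus C3 is not affected, because those subjects are randomised at visit 4.

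**Size if visit 4 were used.** From the documents: n = 60 per group. Assumed, because the documents give none of these:
- R, the ratio of the groups' visit-4 GMTs, 1.0 to 1.3
- equal true visit-5 GMTs
- slope of visit 5 on visit 4, taken equal to its correlation r4, 0.5 to 0.7
- correlation of visit 5 with visit 1, r1, 0.3 to 0.5
- SD of ln titer 1.2 (range 1.0 to 1.4)

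Adjusted ratio = R^(−slope). Lower 95% limit = exp(−slope × ln R − 1.96 × SE), with SE = SD × √(1 − r²) × √(2/60). At SD 1.2, 1.96 × SD × √(2/60) = 0.429.

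| R | Ratio, visit-4 adjusted | Lower limit, visit 4 (r4 = 0.5 / 0.7) | Lower limit, visit 1 (r1 = 0.3 / 0.5) |
|---|---|---|---|
| 1.0 | 1.00 | 0.689 / 0.736 | 0.664 / 0.689 |
| 1.1 | 0.953 / 0.935 | 0.657 / 0.688 | 0.664 / 0.689 |
| 1.2 | 0.913 / 0.880 | 0.629 / 0.648 | 0.664 / 0.689 |
| 1.3 | 0.877 / 0.832 | 0.605 / 0.612 | 0.664 / 0.689 |

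Visit 4 gives the better limit at R = 1.0, the two are about equal at 1.1, and visit 1 is better from 1.2. The break-even R is 1.00 to 1.19 over SD 1.0 to 1.4.

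**Chance that the visit-4-adjusted interval excludes 1.** In simulation over SD 1.0 to 1.4 this was about 5% at R = 1.0, 5–8% at 1.1, 7–17% at 1.2 and 9–29% at 1.3. With visit-1 adjustment it stayed at 4–5%. The 29% needs R = 1.3, slope 0.7 and SD 1.0 together. There the shift is 0.7 × ln 1.3 = 0.184 and SE = 1.0 × 0.714 × 0.1826 = 0.130, so the shift is 1.41 SE and 1 − Φ(1.96 − 1.41) ≈ 0.29. A smaller SD would raise these chances. The shift in the ratio itself does not depend on the SD.

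**Cost of avoiding visit 4.** Interval width on the log scale relative to visit-4 adjustment is √(1 − r1²)/√(1 − r4²) = 1.00 to 1.34 with a visit-1 titer. With no titer covariate it is 1/√(1 − r4²) = 1.155 to 1.40.

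**Comparison with fold rise.** Mean fold rise is also a primary endpoint (section 3.2.1). In year 2 its natural denominator is visit 4. With equal visit-5 GMTs the between-group fold-rise ratio is R^(−1): 0.91, 0.83 and 0.77 at R = 1.1, 1.2 and 1.3. That is a larger shift than visit-4 adjustment produces.

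**The case for a change.** The strongest case for a change is that the visit-1 reading does not help a strain with no visit-1 titer. The analyst must then use visit 4, borrow the titer of a related strain, or drop the covariate, and section 12.2.1 does not say which. The statement in section 8 that HI titers are determined at all time points does not say every strain at every visit. The comparison of GMTs at each time point in the synopsis is untouched by the choice of covariate, but section 12.2.1 takes non-inferiority from the adjusted interval. A sentence in the plan would need no new samples.

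The textual part of this stands: the gap is real for any new strain. It does not establish that the plan is wrong. Having no same-strain baseline leaves a choice open; it does not commit anyone to visit 4. The quoted phrase is also loosely built. The baseline titer may be given as a reason why GMTs differ and not as a fixed covariate, and the list is illustrative. A workable route also exists: section 7.1 has sera frozen and shipped in batches after all draws, so testing visit-1 sera against later strains looks feasible, though it is not planned and would be extra assay work.

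**Conclusion.** No change to the plan follows. This is a gap that an analyst can fill sensibly, followed by a fair trade-off.

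The gap is the unnamed visit. For groups A and B the protocol's own usage fills it with visit 1, and visit-4 adjustment of these groups is nowhere stated. The feared bias therefore belongs to an analysis the plan does not specify, for a set of strains it does not identify and which could be empty.

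The trade-off is between two legitimate questions. Section 1 notes that response depends on pre-existing antibody, so the conditional contrast is a reasonable one to report, provided it is described as such. Barring it costs 0–34% in interval width with a visit-1 titer, or 15–40% with none, and gains nothing in validity if R = 1.0. It would also sit oddly beside a year-2 fold rise taken from visit 4, which moves further with R.

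Under the assumptions shown, the ratio would move by nothing at R = 1.0, by 5–6% at R = 1.1 and by 12–17% at R = 1.3. R, slope and SD are all assumed and the documents state no non-inferiority margin, so they cannot show a changed conclusion. A report that states which visit supplied the covariate for each strain would let a reader judge the result.
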